7.7.1 General considerations

An initial exploratory descriptive analysis will be conducted for each country specific cohort post data extraction to provide insight into general patterns, functional form and any outliers of exposure and covariates. These initial data will be further summarized using descriptive statistics as outlined in the previous section. Additionally, variable distribution will be explored visually using bar charts, boxplots or histograms where relevant.

From the study population, country specific cohorts will be created as detailed in section 7.2.2. Not all cohorts will be possible to be constructed in all databases as they depend on the healthcare setting present in a database. The proportion and summary characteristics of patients excluded from each sub-cohort analysis will be summarized in a STROBE diagram.

7.7.2 Glucocorticoid prescribing patterns (primary objective 1)

Prescribing patterns of systemic glucocorticoids for the treatment of COVID-19 will be summarized by the four cohorts (section 7.2.2) and by subgroups of special interest (section 7.2.4) and the description will include time to initiation of glucocorticoid treatment (from COVID-19 diagnosis), duration of treatment, route of administration, daily dose at start, cumulative dose and duration of

treatment received post COVID-19 diagnosis, see section 7.3.2 for details regarding calculation of exposure parameters .

Frequency of concomitant use of other medications and invasive/non-invasive respiratory support at COVID-19 diagnosis index date and during follow-up will also be presented.

The time to systemic glucocorticoid initiation from COVID-19 diagnosis will be modelled as a time-to-event outcome using the Kaplan-Meier (KM) estimator. The patient follow-up from COVID-19 diagnosis date until systemic glucocorticoid treatment index date will be included in the KM analysis, with start of systemic glucocorticoid therapy being considered a ‘failure’ event. This KM analysis will be stratified by route of systemic glucocorticoid administration (oral vs intravenous). The KM survival function curve (95% CI) and summary statistics of 25th percentile, median, 75th percentile of time to event (in days) will be provided. The survival function within each stratification will be compared using log-rank test.

A time series graph will be used to investigate changes in prescribing patterns over calendar time. Monthly and quarterly incidence steroid incident use will be plotted against time from January 2020 until study end. Key dates (such as Recovery trial) should be highlighted on this graph to allow differentiation between time periods. A formal before /after analysis is not proposed. Results will be stratified per country and per database.

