End of data collection	NA. Data extraction last end date will be the latest available date in each database up to maximum 1st January 2021
Final study report provided to EMA	April 2021

Section 5.0 Rationale and Background

Coronavirus disease 2019 (COVID-19) caused by Severe Acute Respiratory Syndrome Corona virus 2 (SARS-CoV-2) originated in China in December 2019 and was accepted as a global pandemic March 2020. (1) The majority of COVID-19 infections are either asymptomatic or have mild symptoms, however, progression to pneumonia and acute respiratory distress syndrome (ARDS) is reported in 10-20% cases, especially in those of older age or with co-morbidities who are subsequently more likely to be hospitalized and require ventilatory support. (2,3) The overall case fatality rate is hard to estimate in view of rapidly changing data and serious underestimation of cases, however, it is considered to be around 3%. (4) Amongst COVID-19 patients admitted to UK hospitals, the case fatality rate is over 26% overall, and over 37% in patients requiring invasive mechanical ventilation. (5)

According to the current literature, older age and co-morbidities are associated with higher risk of immunologic complications such as macrophage activation syndrome (MAS) and cytokine storm syndrome secondary to, and disproportionate to the severity of Covid-19 infection. (6) Accordingly, there are recommendations that anti-viral treatment should be combined with appropriate immunosuppressive and immunomodulatory drugs since it is hypothesized that early recognition and appropriate treatment of immunologic complications will decrease the morbidity and mortality in COVID-19 patients. (7)

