7.2.3 Follow-up

Two index date definitions will be applied as appropriate for each objective.

- Diagnosis index date is defined as a positive PCR test for SARS-CoV-2 (labCOVID-19) or a confirmed COVID-19 diagnosis(diagCOVID-19) whichever is the earliest.
- Treatment index date is defined as start of first systemic glucocorticoid treatment episode specifically for the treatment of COVID-19, irrespective of whether the patient is a prevalent or naïve user.

Follow up for all patients will begin from the index date until they experience the outcome of interest (endpoint, depending on the objective) or until cohort exit (date of censoring). The patients will be followed up for maximum 90 days or until censoring occurs, censoring criteria are:

- death
- patient exit (deregister) from a contributing data provider (GP practice)
- end of the database's data collection
- end of study period (latest data cut-off)

The lookback window for evaluating risk factors, medical history is 365 days and will be applied only to outpatient cohorts.

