For each sub-cohort and type of person-time the numerator for each time frame will contain the number of patients for whom an outcome has been recorded in that time frame since the onset of that type of person-time. The crude incidence rate of each outcome within the relevant sub-cohort will be expressed as number of cases per 1,000 patient-days at risk.

The cumulative incidence rate will be reported at the end of follow-up (30 and 90 days).

The person-time estimation and the calculation of the crude incidence rate for secondary objectives 2 and 3 will be similar except for the outcomes being considered in each case. For secondary objective 2, adverse events of interest for glucocorticoids (listed in Section 7.3.3) will be the outcome, and for secondary objective 3 mortality and other disease outcomes (Section 7.3.4) will be the outcome.

Both stratification and adjustment will be used as a method to deal with confounders.

In order to examine risk factors of the outcomes of interest, data will also be stratified by subgroups of interest (7.2.4) and stratum-specific crude incidence rates will be calculated. The stratification variables include the healthcare setting, glucocorticoid user type (naive, prevalent) treatment groups and subgroups of special interest.

Separate Cox regression models will be used to estimate adjusted cause-specific HR³ (in order to account for competing events) for each outcome **within** the following four treatment groups:

- Use of systemic glucocorticoids without other treatments for COVID-19 (drug and respiratory support)
- Use of systemic glucocorticoids plus other treatments for COVID-19 (drug and respiratory support)
- Only other treatments and respiratory support with no systemic glucocorticoids

³ Cause-specific HR are to be interpreted as instantaneous risk estimates and not as cumulative risk estimates; cumulative risks estimates are subject to competing events <https://pubmed.ncbi.nlm.nih.gov/30012114/>

- No specific treatments for COVID-19 infection (other concomitant treatments for indications other than for COVID-19 are allowed)

In addition to stratified analysis, for each of the above four treatment groups, two sets of Cox regression models will be run:

- 1) A model that is adjusted for a list of predefined confounders
- 2) A model that is adjusted for a high dimension propensity score that is derived through large-scale modelling, using all available covariates in each dataset (Section 7.7.5)

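### Kaplan-Meier with death censored cannot give hospital glucocorticoid uptake: over all cohort members it overstates the share started, and over starters only it reaches 100% by construction

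*Protocol*

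**What the plan says.** Time from COVID-19 diagnosis to glucocorticoid initiation is one of the variables of the primary objective (Protocol 6.2). Section 7.7.2 fixes the estimator: "The time to systemic glucocorticoid initiation from COVID-19 diagnosis will be modelled as a time-to-event outcome using the Kaplan-Meier (KM) estimator", "with start of systemic glucocorticoid therapy being considered a ‘failure’ event". The planned output is the curve with its 95% CI, and "summary statistics of 25th percentile, median, 75th percentile of time to event (in days) will be provided". The analysis is stratified by oral versus intravenous route.

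Two statements bear on who is in the risk set, and they point in different directions:

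- Section 7.2.3: "Follow up for all patients will begin from the index date until they experience the outcome of interest" or are censored. It adds "The patients will be followed up for maximum 90 days or until censoring occurs, censoring criteria are", and death is the first item in that list.
- Section 7.7.2: "The patient follow-up from COVID-19 diagnosis date until systemic glucocorticoid treatment index date will be included in the KM analysis". A patient who never starts has no treatment index date and no route.

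Competing events are addressed only for secondary objectives 2 and 3, in 7.7.4: "Separate Cox regression models will be used to estimate adjusted cause-specific HR". A footnote there warns that cumulative risks are affected by competing events. Nothing comparable is said for the time-to-initiation analysis.

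**The concern.** A patient who dies without a glucocorticoid can never start one. Kaplan-Meier with death censored passes that patient's weight to the survivors still at risk, as though the patient would have gone on to start at their rate. The complement of the curve is then not the proportion treated by day t. Its quantiles describe a hypothetical cohort in which nobody dies.

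This matters most in the hospital cohort. Section 5.0 says that in UK hospitals "the case fatality rate is over 26% overall". The study is descriptive, so the estimate is itself the result. The planned 95% CI reflects sampling error and does not cover this bias.

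Stratifying by route adds a second difficulty. Route is known only once treatment has started, so 7.7.2 leaves open where non-starters go. The meaning of the curve depends on that choice.

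**Working it through.** The protocol gives no figure for this analysis, so there is none to reproduce.

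**Inputs from the protocol**
- Kaplan-Meier, curve and quartiles (7.7.2); death censored (7.2.3).
- A start counts as COVID-19 treatment from 2 days before to 30 days after diagnosis (7.3.2.1), so T = 30 days.
- Hospital cohort of around 2,000 patients from one database (7.5).
- UK hospital case fatality over 26% (5.0). This counts all deaths, so it is used only as a ceiling for deaths before any glucocorticoid.

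**Assumptions, not in the protocol**
- Share treated by day 30: c = 30% or 40%.
- Share dying untreated by day 30: d = 3%, 13% (half of 26%) or 26%.
- Constant hazards over the 30 days.
- 1,800 naive hospital patients, used only for the standard error (SE).

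**Reading A: all cohort members at risk, death censored**

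Total cumulative hazard L = −ln(1 − c − d). Initiation part A = L × c/(c + d). Then 1 − KM = 1 − exp(−A), while the true share started is c. SE = √(c(1 − c)/1800), which is 1.08 points at c = 30% and 1.15 points at c = 40%.

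Worked case, c = 0.30 and d = 0.13: L = −ln(0.57) = 0.562; A = 0.562 × 0.30/0.43 = 0.392; 1 − exp(−0.392) = 32.4%, an excess of 2.4 points.

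| Treated c | Untreated death d | 1 − KM at day 30 | Excess (points) | Excess / SE |
|---|---|---|---|---|
| 30% | 3% | 30.5% | 0.5 | 0.5 |
| 30% | 13% | 32.4% | 2.4 | 2.3 |
| 40% | 13% | 43.4% | 3.4 | 3.0 |
| 30% | 26% | 35.6% | 5.6 | 5.2 |
| 40% | 26% | 48.0% | 8.0 | 6.9 |

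*Quantiles.* The KM p-quantile is T × [−ln(1 − p)]/A. The cumulative-incidence quantile is T × [−ln(1 − p(c + d)/c)]/L. In every row 1 − KM stays below 50%, so only the 25th percentile falls inside the 30 days. At 40%/13% it is 15.1 days by KM against 16.0. At 40%/26% it is 13.2 against 14.8.

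The median is affected only if uptake is higher. At 50% treated and 15% untreated death, 1 − KM is 55.4% and the median is 25.7 days against 30.0. A simulation of that case (2,000 patients, 300 replicates) gave 55.4% against 50.0% actually treated, and a KM median of 25.8 days.

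**Reading B: starters only in the route strata**

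Every patient has the event, so death censors nobody. The curve is the empirical distribution of start times and ends at 100%. In the same simulation the quartiles were 5.0, 11.2 and 19.1 days. They describe starters correctly but carry no information on how many patients started.

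**Discharge**

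HM Hospitales covers in-patient care (7.4), and 7.2 captures discharge as an outcome. Discharge is not in the 7.2.3 censoring list. If discharged patients were nevertheless censored, with an assumed 40% treated, 10% dead and 40% discharged untreated: L = −ln(0.10) = 2.303, A = 2.303 × 0.40/0.90 = 1.023, and 1 − KM = 64.1%. Making death alone a competing event would not remove this. The death part is 2.303 × 0.10/0.90 = 0.256, and (1.023/1.279) × (1 − exp(−1.279)) = 57.7%, still well above 40%.

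**The case against.** The strongest reply is that 7.7.2 plans no unstratified curve. The analysis is stratified by route, and the person-time described ends at the treatment index date; both exist only for starters. On that reading the death bias does not arise and the quartiles are valid for starters. This stands as a possible reading. It does not remove the point, because 7.2.3 follows all patients to the outcome or censoring, and the starters-only curve cannot show uptake.

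Second, nothing says uptake will be read off 1 − KM; 7.7 reports categorical variables as counts and percentages. This also stands. A reader might infer that the protocol commits to an inflated uptake figure, and it does not. It does commit to the curve and its quartiles, and over the whole cohort those have the defect shown.

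Third, the size. A reader might take 26% as the share dying untreated. The documents do not support that. It is the fatality from all deaths in UK hospitals, while the cohort comes from a private Spanish network. Section 7.9.1 ties glucocorticoids to severe disease, so many deaths may follow treatment. Section 7.2.2 also excludes patients with intensive services in the 30 days before or on index. With few untreated deaths the excess is about half a standard error or less: at 20% treated and 3% untreated death it is 0.3 points.

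Finally, the scope is narrow: one of eight databases, about 2,000 of 153,759 patients (7.5). Hospital use is nevertheless one of the two settings named in the primary objective.

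**Conclusion.** The point holds conditionally. Over all hospital cohort members, Kaplan-Meier with death censored overstates the share started by day t and gives quantiles equal to or earlier than the true ones. That direction is mathematical and needs no assumed rates. Over starters only, the quartiles are unbiased by death but the curve cannot show uptake. Under neither reading does the planned curve give hospital uptake over time.

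The size cannot be derived from the protocol. Under the assumed constant hazards with 30-40% treated, the excess runs from about 0.5 points to a ceiling of 5.6 to 8.0 points, with 2.4 to 3.4 points in between. It would be larger if more patients were treated. A general claim that all three quartiles are materially shortened is not supported: in the tabulated scenarios only the 25th percentile is reached within 30 days. This should be changed, but it does not undermine the study.

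**What to change.** In 7.7.2, for the hospital cohort:

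- Define the risk set as all cohort members from diagnosis.
- Replace Kaplan-Meier by the Aalen-Johansen cumulative incidence of initiation, with death and discharge before initiation as competing events.
- Treat route (oral, intravenous) as event type and not as a baseline stratum.
- Report the estimate with 95% CI at fixed days up to day 30, the last day on which a start counts under 7.3.2.1.
- Report time quartiles among starters only, labelled as such.

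In the ambulatory databases, treat death as a competing event only where vital status is recorded. Section 7.9.2 says DA Germany, LPD France and LPD Italy do not record it, so state the limitation there.

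The cost is a little more analysis work with a standard estimator, and a somewhat lower reported uptake than 1 − KM would give. The hospital analysis needs no additional data: admission, discharge and death dates are among the HM Hospitales fields described in 7.4.

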- Spain – Information System for Research in Primary Care (SIDIAP) as primary care databases

Hospital:

- Hospital de Madrid Hospitales

Data analysis

Continuous variables will be described using mean, standard deviation, median, first and third quartiles, minimum, and maximum. Categorical variables will be described by the number and percentage of patients in each category. Patterns of missingness will be reported and 95% confidence Intervals will be presented. The

results for each country and where available, each setting will be presented separately.

Primary Objective:

- Descriptive analysis for systemic glucocorticoid use patterns will be carried and stratified by setting, glucocorticoid exposure type (naive, prevalent) and subgroups of special interest.
- Kaplan-Meier methods will be used to estimate time to systemic glucocorticoid initiation from COVID-19 diagnosis, stratified by route of administration (oral vs intravenous).

Secondary Objective 1:

- Cohort-specific descriptive statistics summarizing demographic, health and clinical patient characteristics, stratified by setting, glucocorticoid exposure type glucocorticoid (naive, prevalent), and subgroups of special interest will be presented.

Secondary Objectives 2 and 3:

- Crude incidence (presented as both proportions and rates) for the relevant outcomes for each of the treatment exposure groups will be calculated.
- The cumulative incidence rates will be reported at the end of follow-up (30 and 90 days).
- Data will be stratified by setting, glucocorticoid exposure type (naive, prevalent), and subgroups of special interest
- Cox regression models (using multivariable models and using PS adjustment) will be used to compute the adjusted incidence rates.

Secondary Objective 4:

- The performance of different COVID-19 disease definitions based on rule-based phenotype algorithms will be explored using diagnostic predictive modelling

**Plans for
Disseminating
and
Communicating
Study Results**

IQVIA will produce a study report in accordance with the GVP guidelines VIII (EMA/813938/2011). Study information (including protocol and final report) will be added in the EU PAS register.

Section 3.0 Amendments and Updates

Major and Minor Amendments	
Major Amendments	Minor Amendments

 None 	
 Abstract section Appendix 3 Misspellings and editorial checks across the entire document

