6.2 Primary Objective

To describe utilization of systemic glucocorticoids (e.g., dexamethasone, prednisolone, methylprednisolone or hydrocortisone) for treatment of COVID-19 in two settings: hospitalized (in hospital care) and ambulatory (any care received outside of hospital) within 90 days following COVID-19 diagnosis. The following variables will be described:

- Prevalent use or naïve (incident) use of systemic glucocorticoid at date of diagnosis of COVID-19
- Concomitant use of other medications (number and type) and invasive/non-invasive respiratory support during follow up
- Type of systemic glucocorticoid received
- Time to systemic glucocorticoid initiation from COVID-19 diagnosis
- Route of administration
- Systemic glucocorticoid daily dose at initiation (treatment index date), cumulative duration, distribution of duration of use and cumulative dose of systemic glucocorticoid received
- For prevalent users: proximity of previous glucocorticoid use to COVID-19 diagnosis (current use (concomitant on date of COVID-19 diagnosis, recent use (between 15-30 days before date of COVID-19 diagnosis) or remote use (use ended more than 30 days before date of COVID-19 diagnosis))

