7.3.2.1 Glucocorticoids

Glucocorticoids used in COVID-19 indication

The primary treatment group of interest is based on exposure to systemic glucocorticoids. The following drugs will be considered as being used for COVID-19 diagnosis:

- Dexamethasone (H02AB02)
- Prednisone (H02AB07)
- Prednisolone (H02AB06)
- Methylprednisolone (H02AB04)
- Hydrocortisone (H02AB09)

Only glucocorticoids which were investigated in clinical trials (13,21) or are recommended by clinical guidelines are included (22–24) to avoid misclassification of steroids used for other conditions. As indication is not captured in the available databases, a glucocorticoid treatment will be considered to have been initiated for COVID-19 treatment if:

For incident users

- The glucocorticoid treatment was initiated between 2 before and 30 days after COVID-19 diagnosis date (21)
- It is one of the five glucocorticoids recommended for COVID-19 as above

For prevalent users

- The glucocorticoid treatment was initiated between 2 before and 30 days after COVID-19 diagnosis date
- It is one of the five glucocorticoids recommended for COVID-19 as above
- The glucocorticoid started after COVID-19 diagnosis differs from the chronically used glucocorticoids OR there is a change in dose or schedule of administration compared to the prevalent use, occurred after COVID-19 diagnosis.

Glucocorticoids for pre-existing conditions

For the prevalent users, any steroid in the ATC class H02 glucocorticoids for systemic use will be considered. A patient is defined as a systemic glucocorticoids prevalent user if it has at least one prior exposure to systemic² glucocorticoids in the 120 days prior to diagnosis index date.

For the description of prevalent users of glucocorticoids, categories of use will be created based on proportion of days covered (PDC) during the lookback period. PDC is calculated as the number of days in period covered by prescriptions divided by number of days in the period.

- PDC > 85% as heavy user
- PDC 50-85% as moderate user
- less than 50% PDC as light user

Another categorization of prevalent glucocorticoids user will be based on how recently in the past the last prescription was observed:

- current use (concomitant on date of COVID-19 diagnosis)
- recent use (between 15-30 days before date of COVID-19 diagnosis)
- remote use (use ended more than 30 days before date of COVID-19 diagnosis)

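### Time to glucocorticoid start is stratified and tested by route, which is known only once treatment has started, so the curves describe starters and not diagnosed patients

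*Protocol*

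**What the plan says.** Protocol Section 6.2 lists time from diagnosis to glucocorticoid start among the variables of the primary objective, whose horizon is "within 90 days following COVID-19 diagnosis". Section 7.7.2 gives the method: "The time to systemic glucocorticoid initiation from COVID-19 diagnosis will be modelled as a time-to-event outcome using the Kaplan-Meier (KM) estimator", "with start of systemic glucocorticoid therapy being considered a ‘failure’ event". On the time that enters, it says "The patient follow-up from COVID-19 diagnosis date until systemic glucocorticoid treatment index date will be included in the KM analysis". It continues: "This KM analysis will be stratified by route of systemic glucocorticoid administration (oral vs intravenous". Curves with 95% CIs and the three quartiles of time to event are to be reported, and "The survival function within each stratification will be compared using log-rank test". The data analysis part of the abstract (Section 2.0) repeats the stratification: "Kaplan-Meier methods will be used to estimate time to systemic glucocorticoid initiation from COVID-19 diagnosis, stratified by route of administration (oral vs intravenous".

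Three other sections bear on this:

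- Section 7.2.3 makes the treatment index date the start of the first glucocorticoid episode for COVID-19. It follows all patients for at most 90 days and lists death as a censoring criterion.
- Section 7.3.2.1 attributes a glucocorticoid to COVID-19 by timing: "The glucocorticoid treatment was initiated between 2 before and 30 days after COVID-19 diagnosis date".
- Section 7.3.2.3 defines four exposure groups, two of which receive no systemic glucocorticoid. Patients who never start are therefore expected in the study population.

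**The concern.** A Kaplan-Meier stratum should be a group that can be identified at the time origin and is at risk from then on. Here the origin is diagnosis, but the stratum is a property of the event itself. A patient who never starts a glucocorticoid has no route, and no section says which stratum such a patient joins.

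The results could therefore be misread. Two curves that run to full initiation, with medians given in days, could be taken to show that nearly all diagnosed patients were treated early. A log-rank p-value between oral and intravenous could be taken to show a difference in uptake between the routes. Section 7.7.2 specifies no other method for time to initiation.

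**Working it through.** The protocol states no event count, power or alpha for this analysis, so there is no figure to reproduce. The check is by logic, with an illustration.

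**Inputs.** From the protocol: the event is glucocorticoid start; the strata are oral and intravenous; a qualifying start falls no later than day 30; follow-up is at most 90 days; the hospital database has about 2,000 patients (Section 7.5). Assumed, because the protocol gives no uptake: four pairs of oral/intravenous shares; starts spread evenly over days 0 to 30 (intravenous over days 0 to 15 in the earlier-timing scenarios); no death or other loss before day 30.

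**Step 1: strata of starters only.** The product-limit estimate is S(t) = Π(1 − d/n) over event days. Every member of the stratum has the event, so on the last event day d = n, the last factor is 0 and S = 0. Initiation is 100% by day 30 whatever the true uptake.

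**Step 2: all diagnosed patients.** With no loss before day 30, the estimate is the number of starters divided by 2,000.

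| Assumed share oral / IV | Starters oral / IV | Starters-only strata | All diagnosed, either route | Simulated, all diagnosed (equal timing / IV earlier) |
|---|---|---|---|---|
| 5% / 5% | 100 / 100 | 100% / 100% | 200/2,000 = 10% | 10.2% / 10.7% |
| 10% / 40% | 200 / 800 | 100% / 100% | 1,000/2,000 = 50% | 49.5% / 51.0% |
| 25% / 25% | 500 / 500 | 100% / 100% | 1,000/2,000 = 50% | 49.7% / 50.3% |
| 2% / 30% | 40 / 600 | 100% / 100% | 640/2,000 = 32% | 31.7% / 32.0% |

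In the simulated data the starters-only medians were 7 to 17 days. The median over all diagnosed patients was not reached in 6 of 8 scenarios. In the other two, where uptake just passed 50%, it was day 27 and day 30.

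**Step 3: what the log-rank test sees.** Over 200 replicates per scenario, with equal timing in the two routes, it rejected at the 5% level in 7%, 2.5%, 5% and 4% of replicates (table order). Simulation error is about √(0.05 × 0.95/200) = 1.5 percentage points. These rates stay near 5% whether oral and intravenous starts stand at 1:1, 1:4 or 1:15. When intravenous starters began earlier, it rejected in 100%. The test responds to timing among starters and not to frequency of starting.

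**Step 4: never-starters censored in both strata.** At 5% / 5% there are 2,000 − 200 = 1,800 never-starters. Each stratum has 100 + 1,800 = 1,900 records, so 2 × 1,900 = 3,800 records come from 2,000 patients and 1,800 patients sit on both sides of a test that assumes independent groups. The curves are also wrong for route-specific initiation. At 10% / 40% there are 1,000 never-starters, so the oral curve reaches 200/1,200 = 16.7% against a true 10%, and the intravenous curve 800/1,800 = 44.4% against a true 40%.

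**The case against.** The test is not without content. Among starters it is a legitimate comparison of timing, and with nobody censored the Kaplan-Meier quartiles are ordinary quartiles. To call the test meaningless goes too far.

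A reader might infer that the study cannot say what share of patients started, or that this is its only inferential output. The documents do not support either. Section 7.7 reports categories as numbers and percentages with binomial 95% CIs, from which an overall share can come, and Section 7.7.2 plots monthly and quarterly incident use. The log-rank test is the only hypothesis test in that section, but not its only inference.

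A reader might also add that censoring at death distorts these curves. That cannot be claimed together with the 100% result, because in a stratum of starters nobody dies before treatment. It matters only if never-starters are in the risk set. Section 7.2.3, which follows all patients to event or censoring, lends that reading some support, but then the double counting in Step 4 applies.

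Nor does the 30-day attribution window contradict the 90-day objective. Duration, cumulative dose and concomitant treatment can be described to day 90 for a treatment started by day 30, and the initiation curve is merely flat afterwards. Starts on days −2 and −1 need only a routine derivation rule. For prevalent users, Section 7.3.2.1 also requires the change in treatment to come after diagnosis, so those two days mainly concern naive users.

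These points narrow the concern. None makes the route strata valid groups at risk from diagnosis.

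**Conclusion.** The concern holds in this form: the route-stratified curves, their percentiles and the log-rank test do not describe or compare initiation among diagnosed patients. On the starters-only reading they describe timing among those who started. On the other reading the test is invalid.

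The 100% result follows from the definitions and needs no assumption beyond leaving never-starters out of the strata, which is the assignment the wording of Section 7.7.2 best supports. The gap to true initiation (10% to 50% in the illustration) rests on assumed uptake.

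The plan should be changed, but it would be too strong to call the defect critical. The study is descriptive, the ENCePP checklist records that there is no a priori hypothesis, Section 6.3 puts treatment comparisons out of scope, and no decision depends on this test.

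**What to change.** In Section 7.7.2 and the abstract:

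- Estimate time to initiation in all diagnosed patients within each cohort, stratified only by factors known at diagnosis, such as setting and user type.
- Use cumulative incidence (Aalen-Johansen) with oral start, intravenous start and death before treatment as competing events, reported at fixed days with 95% CIs.
- Delete the route-stratified Kaplan-Meier analysis and its log-rank test. Give timing among starters as plain quartiles by route, labelled as such.
- State that the initiation curve is informative only to day 30, given the attribution window, and enter starts on days −2 and −1 as day 0.
- State the limit on death as a competing event. Section 7.9.2 says that three databases (DA Germany, LPD France, LPD Italy) record no vital status, so there the curve cannot account for it.

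The cost is a few lines of wording, some standard code and the loss of one p-value. No new data are needed.
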